**Background**

Atripla (ATP: FTC/TDF/EFV) was the first antiretroviral (ARV) single tablet regimen (STR), and was the dominant first-line ARV regimen in most western countries from approximately 2008 to 2013, when most of the alternatives were multi-tablet regimens including boosted protease inhibitors. However, ATP has not been recommended as a “preferred” ARV regimen since 2015, due to the availability of potent and well-tolerated integrase strand transfer (ISTI)-based regimens, most of which are available as STRs. Nevertheless, there remain “legacy patients” who take ATP with sustained virological suppression. In some cases, the patients remain on ATP because they take concomitant medication that is not compatible with the CYP 3A4 inhibitors ritonavir or cobicistat used to “boost” protease inhibitors or elvitegravir, or they are taking a proton pump inhibitor and are not candidates for Complera or Odefsey. In the Northern Alberta HIV Program, about 316 of the ~2300 HIV patients were receiving ATP as of December 2017.

While ATP is a good ARV regimen from a virological perspective, it has relatively few drug-drug interactions and it has not been associated with an increased risk of cardiovascular disease (unlike HIV protease inhibitors and abacavir), ATP contains tenofovir disoproxil fumarate (TDF), which is associated with an increased risk of chronic kidney disease and fractures over time, for which a safer alternative, tenofovir alafenamide (TAF) has been developed. Additionally, ATP contains efavirenz (EFV), which is associated with neuropsychiatric toxicity and possibly suicidality. Efv is also not compatible with currently recommended interferon-free anti-HCV therapies for HCV genotypes other than HCV genotype 1.

B/F/TAF (bictegravir/FTC/TAF) is an investigational STR that contains neither TDF nor Efv. B/F/TAF includes TAF and FTC, which are well characterized and approved drugs, and FTC/TAF is arguably the best dual nucleoside backbone currently available (IAS-USA 2016 Guidelines), combined with an investigational ISTI, bictegravir, which does not require a pharmacoenhancer, has minimal drug interactions (Custodio J. CROI 2017), has a very high genetic barrier to resistance (Tsiang M, et al. AAC 2016) and was potent and well tolerated in a phase 2 clinical trial (Sax P, et al. Lancet HIV 2017;4:e154-60) and 4 phase 3 clinical trials. B/F/TAF is smaller in size than ATP and the 3 currently approved STRs containing ISTIs. Four phase 3 trials of B/F/TAF met criteria for virologic non inferiority at 48 weeks of treatment, all of which have been published. In particular, B/F/TAF has significantly fewer side effects than dolutegravir-containing regimens, and no treatment-emergent resistance has been reported in any patient receiving B/F/TAF to date.

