### **Inclusion Criteria**

1. HIV-1 seropositive
2. Age > 21 years
3. Receiving ATP > 2 years as their only ART, with HIV-1 RNA < 50 copies/mL at screening and all HIV-1 RNA tests < 100 copies/mL in the past 18 months
4. No documented resistance mutations to the components of ATP
5. Any CD4 count, but no active AIDS-defining opportunistic infections or cancers
6. HBsAg+ permitted if plasma HBV DNA is unquantifiable and the patient does not have decompensated liver disease

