### **Screening**

1. Medical history (including any HIV resistance testing) and physical examination
2. Labs: CBC-D, CD4, creatinine, phosphorus, albumin, ALT, bilirubin, lipids, CD4, HIV RNA, HBsAg (if last result was negative > 6 mo ago), anti-HCV (if last result was negative > 6 mo ago), UPCR, UACR, DEXA hip and spine
3. Add HBV DNA, HBeAg and anti-HBe for all known to be HBsAg+ (if last result was > 3 mo ago)

4. Add HCV RNA for all known to be anti-HCV+, if last test was negative > 12 months ago
5. Add FibroScan for all HCV RNA+ and/or HBsAg+
6. EFV related symptom scores

Any labs performed for standard of care within 30 days of screening visit will be considered baseline results and used to determine inclusion/exclusion criteria.

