### **Study Intervention**

Randomized 1:1, double-blind treatment with ATP and placebo for B/F/TAF (control arm) or B/F/TAF and placebo for ATP (experimental arm). Study medication (two tabs, one active, one placebo) will be taken once daily at the same time of day and with the same amount of food (or not) that the patient was doing when taking ATP prior to study entry. Patients will take double-blinded study medications for 52 weeks, but the primary efficacy analysis will be based on treatment week (TW) 48 data.

At TW52, patients will be told whether they were taking ATP or B/F/TAF, and offered the option of continuing on B/F/TAF, if they were assigned to that arm, or switching to B/F/TAF if they were in the control group receiving ATP. Gilead will supply B/F/TAF to patients after TW52 until B/F/TAF is covered by the provincial formulary.

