### **Study Flow and Monitoring after Screening**

Patients whose screening lab tests are satisfactory will return within 30 days to initiate double-blinded study therapy. Repeat lab testing will not be done on the day that blinded study therapy is initiated.

Blood will be collected at TW4 ( $\pm$  7 days), TW12 ( $\pm$  30 days), TW24 ( $\pm$  30 days), TW36 ( $\pm$  30 days), and TW48 ( $\pm$  7 days) for HIV RNA.. CD4 and phosphorus will be measured at TW24 and TW48. Lipids will be done at TW48. Creatinine, ALT, and albumin will be measured at TW12, TW24, TW36 and TW48. Urine tests will be done at TW24 and TW48. Samples will be discarded once analyzed and will not be stored for future use. DEXA will be done at TW48. EFV-related symptom scores will be done at TW4.

Physical exams will be completed if needed based on symptoms. Adverse events will be assessed and treatment adherence discussed. Serious adverse events will be collected and reported to Gilead Sciences, Inc and Health Canada. In women of childbearing potential, highly effective birth control is required and pregnancy testing will be performed. Visits will be performed in clinic, via telehealth, or via telephone.

Concomitant medications will be recorded. Prescription drug therapy for osteoporosis is not allowed at enrollment. Antacids (e.g., Tums or Rolaids), the ulcer medication sucralfate, and vitamin or mineral supplements that contain calcium, iron, or zinc are to be taken at least 2 hours before or 2 hours after study drug.

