### **Breaking the Blind**

In the event of a medical emergency, the investigator will be able to obtain treatment assignment of each participant.

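### Does admitting HCV-viraemic patients to a blinded efavirenz comparison undermine the trial, given the protocol's own statement about efavirenz and HCV therapy?

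*Protocol*

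**What the plan says.** The Background lists drawbacks of staying on Atripla (ATP). One of them is that "Efv is also not compatible with currently recommended interferon-free anti-HCV therapies for HCV genotypes other than HCV genotype 1". Genotype 1 is outside that statement.

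The Inclusion and Exclusion Criteria do not mention HCV. Hepatitis B has its own condition: "HBsAg+ permitted if plasma HBV DNA is unquantifiable and the patient does not have decompensated liver disease". The Screening section covers HCV by testing: "Add HCV RNA for all known to be anti-HCV+, if last test was negative > 12 months ago" and "Add FibroScan for all HCV RNA+ and/or HBsAg"+. It lists no HCV genotype test, but it does include a medical history.

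On the length of blinding, Study Intervention says: "Patients will take double-blinded study medications for 52 weeks, but the primary efficacy analysis will be based on treatment week (TW) 48 data". Assignment is disclosed at week 52, when every participant may continue on or move to B/F/TAF.

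Study Flow and Monitoring says "Concomitant medications will be recorded" and sets specific rules for osteoporosis drugs, antacids, sucralfate and mineral supplements, but none for HCV antivirals. Stopping Criteria contains general grounds (the investigator's safety judgement and the participant's request) and nothing specific to HCV. Breaking the Blind says: "In the event of a medical emergency, the investigator will be able to obtain treatment assignment of each participant".

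**The concern.** The protocol names an interaction that depends on the arm, expects patients to whom it could apply, and then does not mention it again. A viraemic participant with a genotype other than 1 might need HCV therapy before week 52. Whether that therapy is compatible with the study drug then turns on an assignment that nobody at the site knows, and planned HCV therapy is not obviously a medical emergency.

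Two things would be at stake. The first is the participant, who might wait or might be treated without compatibility being known. The second is the comparison. If assignment were disclosed for this purpose, only participants found to be on ATP would face the conflict. HCV treatment, discontinuation and missing week-48 values could then differ by arm for a reason tied to assignment. That would touch the primary comparison of change in urine albumin/creatinine ratio (UACR) and the week-48 secondary endpoints.

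**Working it through.** **The sections side by side**

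| Question | What the protocol provides |
|---|---|
| Is there an incompatibility? | Yes, for genotypes other than 1 (Background) |
| Can viraemic patients enter? | Yes: foreseen in Screening, no criterion against it |
| Does any section permit HCV therapy alongside blinded drug? | No section says so |
| Can a patient be left out before randomisation? | Yes, by investigator discretion over commitment to study requirements (Exclusion Criteria, item 9) |
| Can treatment stop without opening the blind? | Yes, by safety judgement or participant request (Stopping Criteria) |
| When is assignment known? | At week 52 for everyone; earlier in an emergency |

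No two rows contradict each other. What is missing is a sentence saying which of the available courses is taken.

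**Is the exposure new?** Inclusion requires more than 2 years on ATP as the only antiretroviral regimen. Every participant has therefore lived with the same efavirenz constraint before entry, and the control arm meets no drug conflict that it did not already have. The constraint can be revisited at week 52.

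**Does the arm-imbalance argument hold?** It needs the assignment to be known before HCV treatment is decided. Breaking the Blind provides for disclosure in an emergency. If planned HCV therapy is not an emergency, assignment stays concealed and handling cannot depend on it. The premise that unblinding is unavailable and the premise that unblinding creates the imbalance cannot both be used.

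**How many participants?** The protocol gives neither HCV prevalence nor genotype mix, so both are assumed: viraemia 2% to 15%, share with a genotype other than 1 of 20% to 50%. From Sample Size, N = 200.

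- Affected = 200 × prevalence × share
- Low: 200 × 0.02 × 0.20 = 0.8
- High: 200 × 0.15 × 0.50 = 15
- Chance of at least one = 1 − (1 − p)^200. With p = 0.004 this is 0.551; with p = 0.075 it is nearly 1.

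These are counts of people with the condition. The number starting HCV therapy before week 52 is smaller by a factor that the protocol does not give.

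**What would it cost?** The protocol states no alpha, power, effect size or SD, so the 200 cannot be reproduced. For scale, take two-sided alpha 0.05 and 100 per arm.

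- Detectable difference at 80% power = (1.960 + 0.842) × √(2/100) = 0.40 SD; at 90% power, (1.960 + 1.282) × √(2/100) = 0.46 SD
- Power for 0.40 SD = Φ(0.40 × √(n/2) − 1.960)
- n = 100: Φ(0.868) = 0.807
- n = 99.5 (0.8 of 200 lost): 0.806
- n = 92.5 (15 of 200 lost): 0.777

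For the imbalance, suppose the worst. Half of the 15 are in the ATP arm, all of those are lost, none is lost in the other arm, and those lost differ from those kept by a full 1 SD. The ATP mean then shifts by 7.5/100 × 1 SD = 0.075 SD, compared with a detectable 0.40 SD. At the low end it shifts by 0.4/100 × 1 SD = 0.004 SD.

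**The case for a change.** The best case for a change is that eligibility, concomitant-medication and unblinding rules belong in a protocol and cannot be left to a statistical analysis plan. This protocol does regulate interactions, down to antacids, yet omits the one that its own Background names. It gives hepatitis B a condition and HCV none. Genotype decides whether the conflict exists, yet Screening does not ask for it. Under most of the assumed range at least one affected participant is likely to be enrolled. The general stopping grounds do not say how safety is to be judged when the arm, and with it the interaction, is unknown.

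The factual part of this stands: the handling of HCV therapy in the blinded period is not written down, and a sentence on it would do no harm. The inference from that gap to a compromised trial does not stand. The effect is conditional on viraemia, on a genotype other than 1, and on HCV therapy starting before week 52. The courses open to the investigator include some that leave the blind intact.

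An added sensitivity analysis that drops values after the start of HCV therapy would not help. It selects on an event after randomisation, which is a weakness if that event differs by arm. The choice of such analyses is in any case normal content for an analysis plan that is not shown here.

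**Conclusion.** No change to the plan follows. The protocol is silent on a foreseeable situation, but it states no rule or figure that leads to a wrong result. The investigators set out the interaction themselves and have general means of dealing with it under the blind; which course they take is a clinical matter for them and the sponsor.

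On the assumed ranges, about 0.8 to 15 of 200 participants could have the relevant infection, and fewer would start HCV therapy in time to matter. Losing all of them costs at most about 3 percentage points of power (80.7% to 77.7% for 0.40 SD). A deliberately harsh one-arm loss moves the ATP mean by at most 0.075 SD.

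This rests on the assumed prevalence and genotype share, on alpha 0.05, and on assignment not being disclosed routinely for planned HCV therapy. If disclosure for that purpose became common practice, the question of differential dropout would need to be looked at again.

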### **Benefit risk assessment**

Adverse events are expected to be low frequency and similar to or lower than other HIV regimens. Potential benefits include ongoing suppression of HIV and fewer side effects. Risk/Benefit ratio is favourable.

### **Study Design**

Randomized, double-blind, placebo-controlled comparison of the efficacy and safety of switching to B/F/TAF or remaining on ATP in HIV+ adults who have been receiving ATP for > 2 years with virologic suppression. After a 52-week period of blinded study therapy, participants will be offered open-label B/F/TAF until it is covered by the provincial drug plan.

### **Inclusion Criteria**

1. HIV-1 seropositive
2. Age > 21 years
3. Receiving ATP > 2 years as their only ART, with HIV-1 RNA < 50 copies/mL at screening and all HIV-1 RNA tests < 100 copies/mL in the past 18 months
4. No documented resistance mutations to the components of ATP
5. Any CD4 count, but no active AIDS-defining opportunistic infections or cancers
6. HBsAg+ permitted if plasma HBV DNA is unquantifiable and the patient does not have decompensated liver disease

### **Exclusion Criteria**

1. Pregnancy, breastfeeding or planned pregnancy in the next 2 years
2. Documented resistance to the components of ATP
3. Active AIDS-defining opportunistic infection or cancer
4. Cancer in past 3 years, except non melanoma skin cancer
5. Active psychotic disease or active depression that may interfere with study participation according investigator discretion
6. Any illness with a life expectancy less than 2 years
7. eGFR < 50 mL/min
8. Urine protein/creatinine > 40 mg/mmol
9. Patients who the investigator feels are unlikely to commit to the study requirements for any reason
10. Prescription drug therapy for osteoporosis (calcium and/or vitamin D is allowed)

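### The resistance criteria cover only the components of ATP, so documented integrase-inhibitor resistance does not bar a patient from B/F/TAF

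*Protocol*

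**What the plan says.** Resistance enters eligibility in two places in the Protocol. Inclusion Criteria, item 4, requires "No documented resistance mutations to the components of ATP". Exclusion Criteria, item 2, excludes "Documented resistance to the components of ATP".

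The Background defines the control regimen as "Atripla (ATP: FTC/TDF/EFV" and the experimental regimen as follows: "B/F/TAF (bictegravir/FTC/TAF) is an investigational STR that contains neither TDF nor Efv". It describes the FTC/TAF backbone as "combined with an investigational ISTI, bictegravir", so the third agent of the experimental regimen belongs to a class that ATP does not contain.

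Inclusion 3 sets the treatment history: "Receiving ATP > 2 years as their only ART", with recent viral load suppression. Screening, item 1, is "Medical history (including any HIV resistance testing) and physical examination". Study Intervention allocates participants 1:1 and, at week 52, offers B/F/TAF to those who had been on ATP.

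**The concern.** In a switch study, the resistance record that matters most for the new treatment is the record against the new treatment. Here the rule looks backwards. It confirms that nothing is documented against the regimen that is already working and asks nothing about the drug that is being introduced.

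A patient whose file shows integrase-inhibitor resistance therefore meets every written criterion. One-to-one allocation gives that patient a one-in-two chance of a blinded switch to a regimen whose third agent may be compromised. If allocated to ATP, the same patient is offered B/F/TAF after week 52. What is at stake is the safety of an individual participant, and the risk could be avoided with information the site already holds.

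**Working it through.** No arithmetic applies, because the Protocol gives no figure on this point. The check sets the components of each regimen against the two resistance criteria and then looks for any other rule that would close the gap.

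**Step 1: component by component.**

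| Component | In ATP | In B/F/TAF | Reached by inclusion 4 / exclusion 2 |
|---|---|---|---|
| Emtricitabine (FTC) | yes | yes | yes, directly |
| Tenofovir | yes (as TDF) | yes (as TAF) | yes, through TDF |
| Efavirenz | yes | no | yes, directly |
| Bictegravir (integrase inhibitor) | no | yes | no |

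The tenofovir row rests on reading TDF and TAF as two forms of the same drug, which is how the Background names them. On that reading, one of the three components of the experimental regimen falls outside both criteria, and it is the only one new to the participant.

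**Step 2: does the second statement add anything?** Inclusion 4 and exclusion 2 are the same condition, worded once positively and once negatively. The repetition adds no coverage.

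**Step 3: does another eligibility criterion cover it?**

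- No other inclusion or exclusion item names bictegravir, integrase inhibitors or the components of B/F/TAF.
- The only general discretionary exclusion, item 9, is "Patients who the investigator feels are unlikely to commit to the study requirements for any reason". It concerns commitment, not viral resistance.
- Suppression under inclusion 3 is suppression on a regimen with no integrase inhibitor, so it says nothing about susceptibility to one.
- The investigator's safety judgement under Stopping criteria concerns continuing treatment, so it acts only after the switch has been made.

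**Step 4: does the treatment history make the case impossible?** Inclusion 3 can be read in two ways: ATP has been the sole regimen for more than two years, or ATP is the only antiretroviral treatment ever taken. Study Design speaks only of more than two years on ATP with suppression and does not limit what came before. On the first reading, an earlier integrase-inhibitor regimen is possible. On the second, it is not, but resistance already present at infection would still not be excluded.

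**Step 5: is the information available?** Yes. Existing resistance tests are part of the screening history. The only written rules that act on them are the two limited to ATP.

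**The case against.** The strongest reply is that the gap is almost empty. The Background calls bictegravir investigational, credits it with a very high genetic barrier and reports no treatment-emergent resistance on B/F/TAF, so a record of resistance to bictegravir itself is hardly to be expected. The realistic case is resistance to the class, and the documents do not say how far that carries over to bictegravir. The population points the same way: the Background describes legacy patients from a period when ATP was the dominant first-line regimen and most alternatives were multi-tablet regimens, including boosted protease inhibitors. There are also partial safeguards. The investigator sees any resistance test before randomisation, HIV RNA is measured at weeks 4, 12, 24, 36 and 48, and two consecutive results above 100 copies/mL are a stopping criterion.

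Most of this stands, and it limits the weight of the point. It makes affected patients rare without making them ineligible. The statements on barrier and emergent resistance concern resistance arising on treatment, not resistance documented at entry. Viral load monitoring and the stopping rule limit harm only after the switch.

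A reader might also infer that the gap biases the week 48 comparison of HIV-1 RNA below 50 copies/mL against B/F/TAF, since any resulting failure in the blinded period would fall in that arm. The documents do not support this. Under 1:1 randomisation, such patients are expected equally in both arms. If they fail only on B/F/TAF, that is a real effect of the switch in the population the criteria admit. The comparison remains valid; the question is which population should be exposed. Nor can a size be put on any shift in the response rate, because the Protocol gives neither a prevalence nor a failure risk for such patients.

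**Conclusion.** The point holds as a minor and inexpensive improvement to eligibility. As written, a patient with documented integrase-inhibitor resistance is eligible, may be randomised to B/F/TAF, and may be offered it after week 52 if allocated to ATP. The size cannot be derived from the documents. The number affected is probably small and may be zero.

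The conclusion rests on two things: that tenofovir resistance is covered through TDF, and that inclusion 3 does not by itself rule out such a patient, which Step 4 shows it does not on either reading. It does not depend on how often class resistance affects bictegravir, since the Protocol already treats documented resistance to a regimen's components as a reason not to enrol and merely applies that principle to one of its two regimens.

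The finding concerns individual safety only. The randomised comparison is not biased, and nothing here touches the primary analysis of change in urine albumin/creatinine ratio. Eligibility is fixed in the protocol, so this is not a detail that could be left to an analysis plan.

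**What to change.** The sponsor should reconcile inclusion 4 and exclusion 2 with the experimental regimen described in the Background and Study Intervention. Both criteria should refer to documented resistance to the components of either ATP or B/F/TAF. The wording should make clear whether documented resistance to the integrase-inhibitor class counts, because a rule naming bictegravir alone could leave the realistic case undecided.

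The cost is a few words in two eligibility lines. No new test or visit is needed, since the rule would use the resistance history already reviewed at screening. The downside is that a very few candidates may be excluded.
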